12.2 RECIST

RECIST offers a simplified, conservative, extraction of imaging data for wide application in clinical trials. They presume that linear measures are an adequate substitute for two-dimensional methods and register four response categories.¹⁹⁰

Target Lesions (Main Tumor)

- **Complete Response (CR):** Disappearance of all target lesions. Any pathological lymph nodes (whether target or non-target) must have reduction in short axis to <10 mm.
- **Partial Response (PR):** At least a 30% decrease in the sum of the diameters of target lesions, using the baseline sum diameters as the reference.
- **Progressive Disease (PD):** At least a 20% increase in the sum of the diameters of target lesions, using the smallest sum on study (includes the baseline sum) as the reference. In addition to the relative 20% increase, the sum must also demonstrate an absolute increase of at least 5 mm. (Note: the appearance of one or more new lesions is also considered progression)
- **Stable Disease (SD):** Neither sufficient shrinkage to qualify for PR nor sufficient increase to qualify for PD, using the smallest sum diameters while on study as the reference.

Non-Target Lesions (Lymph Nodes)

- **CR:** Disappearance of all non-target lesions and normalization of tumor marker levels. All lymph nodes must be non-pathological in size (<10 mm short axis).

Note: If tumor markers are initially above the upper normal limit, they must normalize for a patient to be considered in complete clinical response.

- Non-CR/Non-PD: Persistence of one or more non-target lesion(s) and/or maintenance of tumor marker levels above the normal limits.
- PPD: Appearance of one or more new lesions and/or *unequivocal progression* of existing non-target lesions. *Unequivocal progression* should not normally trump target lesion status. It must be representative of overall disease status change, not a single lesion increase.
- Although a clear progression of “non-target” lesions only is exceptional, the opinion of the treating physician should prevail in such circumstances, and the progression status should be confirmed at a later time by the review panel (or principal investigator).

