12.3 Modified irRC, derived from RECIST 1.1¹⁹¹

This new classification is based on recent clinical studies showing delays in tumor regression or stabilization with cancer immunotherapies. For the ENSIGN trial, the concepts of the irRC are combined with RECIST 1.1 to come up with the modified irRC, which uses unidimensional measurements. For modified irRC, only target and measurable lesions are taken into account. In contrast to RECIST 1.1, the modified irRC criteria (a) require confirmation of both progression and response by imaging at eight 8 weeks after initial imaging (evidence of cancer progression within the first 3 months on bone scan only should be interpreted with extreme caution due to risk of tumor flare) and (b) do not necessarily score the appearance of new lesions as PD if the sum of the diameters of target lesions (minimum of 10 mm per lesion, maximum of 5 target lesions, maximum of 2 per organ) and measurable new lesions does not increase by $\geq 20\%$. The same assessment method and technique should be used to characterize each identified and reported target lesion(s) at baseline, during the trial, and at EOT. All measurements should be recorded in metric notation. The modified irRC based on RECIST 1.1 are displayed below. Modified irRC are defined as follows:

- New measurable lesions: Incorporated into tumor burden.
- New non-measurable lesions: Do not define progression but preclude irCR.
- Overall irCR: Complete disappearance of all lesions (whether measurable or not) and no new lesions. All measurable lymph nodes also must have a reduction in short axis to 10 mm or less.
- Overall irPR: $\geq 30\%$ decrease in the sum of the longest diameters of target and new measurable lesions.
- Overall irSD: Neither sufficient shrinkage to qualify for irCR or irPR (compared to baseline) nor sufficient increase to qualify for irPD (compared to nadir), using the sum of the longest diameters of target and new measurable lesions.
- Overall irPD: $\geq 20\%$ increase in the sum of the longest diameters of target and new measurable lesions increases (compared to nadir), confirmed by a repeat, consecutive observation at least 6 weeks (normally it should be done at 8 weeks) from the date first documented.

Documentation of immune-related PD (based on modified irRC) does not mandate discontinuation of the study treatment even after irPD is confirmed with CT scan 6 weeks after the initial observation of irPD.

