Appendix D: Modified irRC, derived from RECIST 1.1

Overall responses derived from changes in index, non-index, and new lesions

Measurable Response	Non-Measurable Response		Overall Response Using Modified irRC
Index and New, Measurable Lesions (Tumor Burden)	Non-Index Lesions	New, Non-Measurable Lesions	
Decrease 100%	Absent	Absent	irCR*
Decrease 100%	Stable	Any	irPR*
Decrease 100%	Unequivocal progression	Any	irPR*
Decrease \geq 30%	Absent / Stable	Any	irPR*
Decrease \geq 30%	Unequivocal progression	Any	irPR*
Decrease < 30% to increase < 20%	Absent / Stable	Any	irSD
Decrease < 30% to increase < 20%	Unequivocal progression	Any	irSD
Increase \geq 20%	Any	Any	irPD

* Assuming that the response (irCR and irPR) and progression (irPD) are confirmed by a second, consecutive assessment at least 4 weeks apart (normally it should be done 6 weeks apart).

Key Milestones:

FPFV / First Dose:

LPLV / Last Subject completed:

Database Lock:

Final Report:

Sponsoring Department: HMHCC &HMHRI

Prepared by: _____

Date _____

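### The modified irRC sum uses longest diameters with no lymph-node exception, while nodes are judged by short axis for irCR and CR, so a normalised node can be scored irSD

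*Combined protocol and SAP*

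**What the plan says.** Both RECIST 1.1 and the modified irRC are used for the primary endpoint, ORR (sections 4 and 12.1).

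- **Section 12.3, irPR:** at least a 30% "decrease in the sum of the longest diameters of target and new measurable lesions".
- **Section 12.3, irSD:** "using the sum of the longest diameters of target and new measurable lesions". The irPD bullet uses the same sum, with a 20% increase from nadir.
- **Section 12.3, irCR:** all lesions gone and no new ones, followed by "All measurable lymph nodes also must have a reduction in short axis to 10 mm or less".
- **Section 12.2, CR:** "Any pathological lymph nodes (whether target or non-target) must have reduction in short axis to <10 mm".
- **Section 12.2, PR:** a 30% "decrease in the sum of the diameters of target lesions, using the baseline sum diameters as the reference". The axis is not named.
- **Appendix D:** irCR appears only in the row with a 100% decrease in measurable burden. That row makes no allowance for nodes.

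No section says which axis of a node enters the sum, or how a node that has become normal is to be entered.

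**The concern.** Within one list of definitions the measured axis changes. Complete response depends on a node's short axis, while partial response, stable disease and progression depend on the longest diameter of whatever is in the sum. A node can lose its pathological short axis while staying fairly long. The sum then falls by less than 30% although the node meets the nodal condition for irCR. Since irSD is a non-response and irCR a response, two careful readers could give the same scan opposite values on the primary endpoint.

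Section 12.3 lists its contrasts with RECIST 1.1 as confirmation and the handling of new lesions. It does not list a different treatment of nodes, so the effect looks unintended. Nodal disease is foreseen: section 12 gives endobronchial ultrasound as the biopsy route for adenopathy.

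**Working it through.** **1. The plan's own figures.** From section 15.1: n = 16, null ORR 3%, alternative 25%; and n = 9, null 3%, alternative 30%; both one-sided at 0.05. With an exact one-sample binomial:

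- NSCLC: P(X ≥ 2 | 16, 0.03) = 0.0818, too large; P(X ≥ 3 | 16, 0.03) = 0.0113. Threshold 3 of 16; power P(X ≥ 3 | 16, 0.25) = 0.8029 (stated: 80.3%).
- Uveal melanoma: P(X ≥ 1 | 9, 0.03) = 0.2398, too large; P(X ≥ 2 | 9, 0.03) = 0.0282. Threshold 2 of 9; power P(X ≥ 2 | 9, 0.30) = 0.8040 (stated: 80.4%).

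Both stated powers reproduce, so the thresholds are 3 and 2 responders.

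**2. One node under the two measurements.** The sizes are assumptions, because the documents give none. Change = (after - before) / before.

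| Node, long x short (mm) | Longest diameter | Short axis |
|---|---|---|
| 28 x 16 to 21 x 9 | (21 - 28)/28 = -25.0% | (9 - 16)/16 = -43.8% |
| 18 x 15 to 14 x 10 | -22.2% | -33.3% |
| 22 x 16 to 16 x 9 | -27.3% | -43.8% |
| 20 x 15 to 13 x 10 | -35.0% | -33.3% |
| 25 x 20 to 14 x 9 | -44.0% | -55.0% |

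The first three nodes meet the nodal condition for irCR in 12.3 but give irSD on longest diameter if the node is the whole sum. The last two give irPR on either axis. The second node, ending at exactly 10 mm, also meets the cut-off in 12.3 but not the one in 12.2.

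**3. The definitions side by side.** Take the first node as the only lesion. The nodal clause of the irCR bullet adds something only if a node may remain visible; otherwise disappearance of all lesions already covers it. On that reading the patient is irCR. Appendix D withholds irCR because the burden has not fallen by 100%, and the sum rule gives irSD.

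**4. How nodal the burden must be.** Let w be the node's share of the baseline sum of longest diameters. If every other lesion disappears and the node shrinks by 25%, the total decrease is (1 - w) + 0.25w = 1 - 0.75w. This stays at or above 30% while w ≤ 0.70/0.75 = 0.933. With everything else gone, the patient becomes irSD only if the node makes up more than about 93% of the sum; otherwise the result is irPR, still a response. If the other lesions shrink only partly, a smaller nodal share can hold the total below 30%. That patient would not be irCR in any case, so the dispute there is only over which axis belongs in the sum.

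**5. Effect of one lost responder.** A single loss reverses the test only when the true count equals the threshold:

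- P(X = 3 | 16, 0.25) = 0.8029 - 0.5950 = 0.208, about 21%.
- P(X = 2 | 9, 0.30) = 0.8040 - 0.5372 = 0.267, about 27%.

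These are conditional on a loss occurring. As an illustration only, if 5% to 20% of true responders were lost, the ORR would be 23.75% to 20% in NSCLC (power 77.0% to 64.8%) and 28.5% to 24% in uveal melanoma (power 77.6% to 67.5%). The documents support no particular share.

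**The case against.** The strongest reply is that this is a narrow case. The sum covers only target lesions and new measurable ones, and that nodes enter it is inferred from the missing exception. The headings in 12.2 pair target lesions with the main tumor and non-target lesions with lymph nodes. Up to five target lesions are allowed, so a purely nodal sum may be uncommon. For uveal melanoma, section 1.1 lists liver, lung, bone and skin as metastatic sites, not nodes. The Appendix D point and the cut-off difference mostly move a patient between irCR and irPR, which leaves ORR unchanged. RECIST 1.1 is applied as well.

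Most of this stands, and it limits the size. It does not remove the conflict: 12.2 expressly allows nodes to be target lesions, and 12.3 speaks of measurable nodes.

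A reader might also infer that the rule creates false progression, because a small normal node could add its longest diameter to the sum. The documents do not support that. Nothing says a non-pathological node is a new lesion, the 10 mm minimum in 12.3 is attached to target lesions, and irPD needs a confirming observation. Nor should the chance of a count one below the threshold be added to the figures in step 5: a lost response matters only at the threshold itself.

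**Conclusion.** The inconsistency is real and affects one of the two criteria for the primary endpoint. Followed as written, 12.2, 12.3 and Appendix D can give a patient with a wholly or mainly nodal burden contradictory responder status. The direct conflict between irCR and irSD needs a nearly all-nodal sum (above about 93% in the worked example).

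The 21% and 27% assume the design ORRs, that the modified irRC count is the one tested, and that a responder has been lost; they are not probabilities that nodal scoring changes the trial's result. The sample-size calculation is unaffected. It would be too strong to conclude that nodal responses will generally be missed, since many node shapes give irPR on either axis. This should be corrected before responses are read, but it does not threaten the design.

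**What to change.** - In 12.3 and Appendix D, define the burden as the longest diameters of non-nodal lesions plus the short axes of lymph nodes. Section 12.2 leaves the axis of its sum open, so the same sentence would serve there.
- In Appendix D, let irCR be met when all non-nodal lesions are gone and all nodes are below the nodal short-axis cut-off. This is needed as well, because changing the axis alone does not rescue every node: 16 x 12 mm to 12 x 9 mm is -25% on both axes, and a node ending at 10 mm has fallen by 30% only if its short axis began at 10/0.7 = 14.3 mm or more.
- Use one nodal short-axis cut-off in 12.2, 12.3 and Appendix D.
- State that a node already non-pathological by that cut-off when lesions are selected, or when it is first seen, is not counted as a target or new measurable lesion.

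The cost is wording in these sections and one CRF field for the short axis of nodes. No extra imaging is needed.

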Treatment with other systemic/local anticancer agents (chemotherapy, immunotherapy, RT, hormone therapy, targeted or biologic agents) other than the protocol treatment is not permitted until disease progression is documented per modified irRC. Concomitant therapies will be continuously monitored from the first day of treatment.

11. Visit schedule and assessments

Visit	Screening ^a	Baseline ^b	V1	V2	V3	V4	V5	V6	V7	V8	V9	V10*	EOT
Day	-28 to -1	-7 to -1	0±5	2±5	4±5	7±5	9±5	11±5	17±5	45±5	73±5	101*±5	
Informed Consent	X												
Inclusion/Exclusion	X												
Demographics	X												
Medical History	X												
Physical Exam ^c	X		X						X	X	X	X	X
Height	X												
Weight	X		X						X	X	X	X	X
ECOG PS	X		X						X	X	X	X	X
12-Lead ECG and MUGA Scan or Echocardiogram ^d	X												X
Concomitant Therapies			Continuous from the first day of treatment										
Hematology ^e	X		X						X	X	X	X	X
Clinical Chemistry ^e	X		X						X	X	X	X	X
PT/INR/aPTT ^e	X								X	X	X	X	X
Serum Pregnancy (β-hCG) ^f	X												
Brain MRI ^g	X												
Tumor Assessments (RECIST 1:1 and irRC) ^h	X												X
Biopsy ⁱ			X						X				
Correlative Studies Blood Collection ^j	X								X		X		
Adverse Events and Serious Adverse Events			From informed consent signing up to and including 30 days after the last treatment dose ^l										
ADV/HSV-tk Administration ^k			X										
Valacyclovir Administration ^k			X										
SBRT Administration ^k				X	X	X	X	X					
Nivolumab Administration ^k									X	X	X	X	

Abbreviations: aPTT = activated partial thromboplastin time; AE = adverse event; ADV/HSV-tk = adenovirus-mediated expression of herpes simplex virus thymidine kinase; ANC = absolute neutrophil count; β -hCG = beta-human chorionic gonadotropin; CBC = complete blood count; CT = computed tomography; ECG = electrocardiogram; ECOG PS = Eastern Cooperative Oncology Group performance status; EOT = end of treatment; INR = international normalized ratio; irRC = immune-related response criteria; MRI – magnetic resonance imaging; MUGA, multigated acquisition; PET = positron emission tomography; PT = prothrombin time; RECIST = Response Evaluation Criteria in Solid Tumors; SAE = serious adverse event; SBRT = stereotactic body radiation therapy; WBC = white blood cell. A window of \pm 5 days is allowed for study visits and assessments (except as otherwise specified).

^aWithin 28 days prior to ADV/HSV-tk administration on day 0.

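### The modified irRC definition of progression (Section 12.3, Appendix D) omits the 5 mm absolute-increase floor of Section 12.2, without explanation; this matters for nadir sums below 25 mm

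*Combined protocol and SAP*

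**What the plan says.** Section 12.2 (RECIST) gives target-lesion progression two size conditions. The first is relative: "At least a 20% increase in the sum of the diameters of target lesions, using the smallest sum on study". The second is absolute: "In addition to the relative 20% increase, the sum must also demonstrate an absolute increase of at least 5 mm". A new lesion is enough by itself: "the appearance of one or more new lesions is also considered progression".

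Section 12.3 (Modified irRC) takes over the one-dimensional sum and adds measurable new lesions to it. Its target lesions are subject to "minimum of 10 mm per lesion, maximum of 5 target lesions, maximum of 2 per organ". irPD is set at 20% or more, worded as "increase in the sum of the longest diameters of target and new measurable lesions increases (compared to nadir", and must be "confirmed by a repeat, consecutive observation at least 6 weeks (normally it should be done at 8 weeks) from the date first documented". No absolute increase is mentioned. The irPD row of the Appendix D table also gives the 20% threshold alone.

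Section 12.3 names two contrasts with RECIST 1.1. One is that the modified criteria "require confirmation of both progression and response by imaging at eight 8 weeks after initial imaging"; the other is that a new lesion is not automatically progression. Loss of the 5 mm floor is not listed. Section 12.3 also says that irPD, even when confirmed, does not oblige the investigator to stop study treatment. Section 10 says that other anticancer therapy "is not permitted until disease progression is documented per modified irRC".

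**The concern.** When the sum is small, 20% of it is a few millimetres, which ordinary reading variation could produce. Section 12.2 guards against this and Section 12.3 does not. Both listed contrasts make progression harder to call, whereas the unlisted one makes it easier. That points to an oversight, although the documents do not say.

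The reference is the nadir, so responders are the patients most likely to have a small one. The confirming scan helps less than it seems to, because both scans are compared with the same nadir. A nadir is the minimum of several noisy readings and so tends to be too low.

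At stake are any PFS, DoR or CBR computed under modified irRC, and the timing of the Section 10 permission for other anticancer therapy. Scans taken after such therapy begins no longer measure the study regimen alone. With 16 and 9 patients planned (Section 15.1), one or two spurious calls would show in a DoR or PFS summary.

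**Working it through.** **The plan's own figures.** The only design figures are the power statements in Section 15.1. Exact one-sample binomial calculations reproduce them: P(X ≥ 3 | n = 16, ORR 25%) = 0.803 and P(X ≥ 2 | n = 9, ORR 30%) = 0.804. Neither depends on the definition of irPD.

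**Size thresholds.** Let S be the nadir sum in mm.
- irPD (12.3, Appendix D) needs an increase of 0.20 × S.
- RECIST target-lesion PD (12.2) needs an increase of max(0.20 × S, 5).
- The two meet where 0.20 × S = 5, that is at S = 5 / 0.20 = 25 mm.

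| Nadir sum S (mm) | irPD increase (mm) | RECIST increase (mm) |
|---|---|---|
| 10 | 2.0 | 5.0 |
| 14 | 2.8 | 5.0 |
| 20 | 4.0 | 5.0 |
| 24 | 4.8 | 5.0 |
| 25 | 5.0 | 5.0 |
| 30 | 6.0 | 6.0 |

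**Who can reach this range.** A baseline sum of 20 mm that falls 30% reaches 14 mm. The irPD size threshold is then 14 × 1.2 = 16.8 mm, while RECIST requires 14 + 5 = 19 mm. At the 30% response boundary, any baseline sum up to 25 / 0.70 = 35.7 mm comes down to 25 mm or less.

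**False confirmed irPD.** These assumptions are not taken from the documents:
- the true sum never changes;
- reading errors are independent and normal, with SD 0.5, 1.0 or 1.5 mm;
- there is a baseline scan plus six further scans (8-weekly imaging over 12 months gives 52 / 8 = 6.5);
- the nadir is the running minimum;
- irPD needs two consecutive qualifying scans.

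Each setting used 200,000 simulated patients. Entries are for SD 0.5 / 1.0 / 1.5 mm.

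| True sum (mm) | 20% rule alone | 20% rule plus 5 mm |
|---|---|---|
| 10 | 0.9% / 28% / 54% | 0% / <0.1% / 1.3% |
| 14 | <0.1% / 9% / 33% | 0% / <0.1% / 1.3% |
| 20 | 0% / 0.9% / 11% | 0% / <0.1% / 1.3% |
| 30 | 0% / <0.1% / 0.8% | 0% / <0.1% / 0.8% |

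The near-identical results at 30 mm show that the gap at smaller sums comes from the missing floor. The confirmation requirement is already built into every figure.

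**The case against.** The strongest reply is that this is a narrow drafting gap. Several parts of it stand.

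- A reader might infer that patients are called progressed on a single change of 2 to 4 mm. They are not: Section 12.3 and Appendix D both require a confirming scan.
- A reader might infer that modified irRC has become stricter than RECIST. The documents do not support that. Overall it is more lenient: it needs confirmation, a new lesion alone is not irPD, and Appendix D scores unequivocal non-index progression with a stable burden as irSD. It is stricter only on the size threshold, and only for nadir sums below 25 mm.
- A reader might infer that false irPD will cut PFS and DoR short. Section 15.1 does not say which criterion governs either; both criteria are applied, and the RECIST reading keeps its floor.
- The primary endpoint is ORR. A later irPD does not undo a confirmed response, so any effect on ORR is indirect at most.
- irPD does not mandate stopping study treatment, and Section 10 lifts a prohibition without requiring new therapy.
- Very small sums may be uncommon. Section 8.1 asks for an SBRT lesion and another lesion of at least 1 cm, and Section 9.3 selects the largest tumor for SBRT. If both are in the sum, baseline is at least 20 mm, where the false rate is 0% to 11% over the SDs shown. A 10 mm sum needs a single minimum-size lesion or a response.
- The simulation holds the sum stable from baseline, whereas a responder has fewer scans after nadir.

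These points limit the consequences. They do not explain why a criterion described as derived from RECIST 1.1 lacks the floor, and confirmation does not replace it at small sums.

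**Conclusion.** The omission is real and unexplained. For nadir sums below 25 mm, a confirmed rise of less than 5 mm counts as irPD but not as RECIST target-lesion PD; from 25 mm upward the size thresholds are the same. The text and the 25 mm crossover are certain.

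The impact is less certain. The false-call rates rest on assumed reading SDs, a stable true sum and seven scans, and they fall steeply as the sum grows. The documents give no reading SD and no distribution of sums, so the number of affected patients among 16 + 9 = 25 cannot be computed. Effects on PFS, DoR or CBR are conditional on those endpoints being computed under modified irRC. Sample size and power are unaffected. This is a cheap improvement and does not threaten the primary analysis.

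**What to change.** Reconcile Section 12.3 and Appendix D with Section 12.2 in one of two ways.

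1. Carry the same requirement into the irPD measurement definition: a rise of at least 20% over nadir and of at least 5 mm in the sum of target plus new measurable lesions, confirmed as specified.
2. If the omission is intended, list it in Section 12.3 as a third difference from RECIST 1.1 and give the reason.

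The choice should be made with Section 10 in view, since that section relies on the same definition; what it should permit clinically is for the sponsor to decide. In the same edit, reconcile the irPD confirmation interval, which is 8 weeks or at least 6 in Section 12.3 but at least 4 and normally 6 in Appendix D.

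The cost is one clause in each of two places, with no new data and no change to sample size or power. The downside of the first option is slightly later irPD calls for nadir sums below 25 mm.
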